**Notes for Schedule of Activities:**

See Appendix 2 for list and description of samples collected including designation for where analysis will occur, local and/or central laboratory for each analyte.

1. The Screening period may be extended up to two weeks for participants who experience a bleed and require infusion(s) with FIX protein products within 96 hours prior to PF-06838435 infusion (Day 0). The reason for extending the screening period must be documented. If the screening period is prolonged greater than 8 weeks, then the participant will need to repeat all screening tests and a new Subject ID will be assigned.

2. At least 96 hours (4 days) washout for regular factor IX products (or up to 168 hours [7 days] washout period for extended half-life factor IX products) on Day 0 prior to infusion is required. The investigational product should NOT be thawed prior to confirmation from the site staff regarding the participant's washout criteria.

3. Unscheduled visits to monitor safety and changes in FIX activity may be necessary during the study. An unscheduled visit may include, but is not limited to, monitoring of hepatic transaminases, FIX transgene expression (FIX activity), FIX antigen (Ag), CPT™ for peripheral blood mononuclear cells (PBMCs) by enzyme-linked immunospot (ELISPOT). A sample for PAXgene RNA may be collected and stored for analysis at the end of study. Any spare plasma from already collected blood samples may also be stored for repeat or additional testing as needed.

4. Informed consent must be obtained from participants prior to any study-related procedures being performed.

5. Demographics include gender, race, date of birth (month and year only), and ethnicity.

Hemophilia history includes (but is not limited to) the date of diagnosis, severity of disease, genotype, HLA, number of exposures to FIX products, type of FIX products received, current dose and infusion regimen of FIX, last dose of FIX received prior to Screening and the first dose of PF-06838435, number of bleeding episodes and factor infusions in the 52 weeks prior to screening, inhibitor history, and allergy/anaphylaxis history.

If genotype and HLA are not known, sample(s) will be drawn for analysis at Screening. Genotype is not a criterion for inclusion or exclusion. However, a documented genotype known to produce a clinically severe phenotype of hemophilia B is required if the participant is otherwise unable to demonstrate severity.

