13. LFTs – albumin, total bilirubin, direct bilirubin, indirect bilirubin, alkaline phosphatase (ALP), aspartate aminotransferase (AST), alanine aminotransferase (ALT), total protein, gamma-glutamyl transferase (GGT), and lactate dehydrogenase (LDH);

Immunology - CPT™ for PBMC by ELISPOT and PAXgene for RNA. PAXgene samples will be stored for analysis at the end of study.

14. Hepatic transaminases and FIX transgene expression will be monitored twice-weekly or thrice-weekly to detect early changes. Between Weeks 1 and 12 post-vector infusion, monitoring will include LFTs, FIX:C, FIX Ag, CPT™ for PBMC by ELISPOT and PAXgene for RNA. Spare plasma, from already collected blood samples will be stored for repeat or additional tests. Some participants may need more frequent monitoring using unscheduled visits.
15. Activated partial thromboplastin time (aPTT) measured in seconds; TAT will be taken just prior to the infusion of FIX product.
16. Participants should be advised to temporarily suspend prophylaxis regimen after vector infusion until being advised by the Investigator to resume.
17. At Day 0, participants should arrive at the clinic with at least 96 hours (4 days) washout of pd-FIX/rFIX or up to 168 hours (7 days) washout of extended half-life FIX product. Participants will receive a single IV infusion of 100 IU/kg of FIX protein product over 10 (±2) minutes.
18. Blood samples will be collected at pre-infusion, 10 (±2) minutes, 1 hour ± 10 minutes, 3 hours ± 10 minutes, 6 hours ± 10 minutes, and 24 (±1) hours from the start-of-infusion of FIX protein product.
19. Thromboelastography (TEG) and/or rotational thromboelastogram (ROTEM) – Only selected participants at selected sites capable of performing these tests locally.  
CCI  
Blood samples will be collected at pre-infusion and 10 (±2) minutes from the start-of-infusion of FIX protein product on Day 0 and End-of-Study Visits.
20. After the completion of FIX protein product infusion, participants will receive PF-06838435 infused via infusion pump over a period of approximately 60 minutes.
21. Haem-A-QoL, EQ-5D-5L, McGill pain questionnaire, and Hemophilia Activities List (including Changes in Level of Activity) questionnaires will be completed by the participants.  
CCI  
[REDACTED]
23. Immunomodulation See [Appendix 2](#): possible tests below:  
LFT – albumin, total bilirubin, direct bilirubin, indirect bilirubin, ALP, AST, ALT, total protein, GGT, and LDH;  
Coagulation –aPTT, FIX:C, FIX Ag  

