### 4.1.3. Dose Escalation and Expansion

#### 4.1.3.1. Initial Dose Escalation

Dose escalation and dose level expansion strategies are employed in the study based on vector-derived FIX activity levels as well as any immune responses against AAV capsid. There will be no dose escalation if at least 3 participants in any dose level achieve steady-state vector-derived FIX activity levels of  $\geq 40\%$ . Steady-state levels are based on 2 separate vector-derived FIX:C activity level measurements (at least two weeks apart) starting from Week 8-12 with adequate washout (ie, 96 hours for factor IX plasma-derived [pd]- or r-FIX and up to 168 hours for extended half-life recombinant factor IX (rFIX) from FIX product.

Dose escalation will occur under the following scenarios:

1. If neither of the first two participants in a given dose level achieve detectable steady-state vector-derived FIX activity levels above their baseline, then escalation to the next dose level will occur, provided there are no safety concerns; or
2. If less than 3 evaluable dosed participants in a given dose level achieve steady-state vector-derived FIX activity levels between 3% to 40% of normal, then escalation to the next dose level will occur, provided there are no safety concerns.

At least 8 weeks of safety data from at least 3 out of 5 participants in a given dose level will undergo review by the independent DMC prior to infusing the first participant in the next dose level (See [Section 4.1.1](#) for staggering strategy). The decision to dose escalate will require the agreement of Pfizer and DMC.

Dose level expansion will occur for the following scenarios:

1. If at least one of the first two participants at the low or middle dose level achieve steady-state vector-derived FIX activity level above their baseline, then up to an initial 5 evaluable participants will be dosed at the respective dose.
2. If one or both of the first two participants in any dose level achieve circulating vector-derived FIX activity levels above their baseline (without using any FIX product) but with a decline to their baseline levels due to an immune response to vector capsid that is NOT well-managed by corticosteroids, then dose escalation will not occur, and instead up to a total of 5 evaluable participants will be dosed at the respective dose.

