#### 4.1.4. FIX Incremental Recovery

FIX incremental recovery will be measured up to 24 ( $\pm 1$ ) hours post-infusion of FIX protein products to assess time at maximum activity and percent recovery for exogenous FIX activity. The exogenous FIX activity levels will be determined by one-stage clotting assay. Participants are required to have at least 96 hours of washout for pd- or r-FIX or up to approximately 168 hours of washout for extended half-life rFIX prior to FIX incremental recovery test on Dosing Day (Day 0).

FIX incremental recovery assessments will be conducted by collecting blood samples at various time-points up to 24 ( $\pm 1$ ) hours from the start of FIX protein product infusion. Blood samples on Day 0 will be collected pre-infusion, 10 ( $\pm 2$ ) minutes, 1 hour  $\pm 10$  minutes, 3 hours  $\pm 10$  minutes, 6 hours  $\pm 10$  minutes, and 24 ( $\pm 1$ ) hours from the start-of-infusion of FIX protein product.

Samples for thrombin generation assessments will also be collected on Day 0 at pre-infusion and 10 ( $\pm 2$ ) minutes from the start-of-infusion of FIX protein infusion and evaluated by an

CCI performed at the central laboratory. For participants at selected sites depending on the testing capabilities, additional samples for global hemostasis may also be collected at pre-infusion and 10 ( $\pm$ 2) minutes from the start-of-infusion of FIX protein infusion and evaluated by the whole blood TEG and/or rotational thromboelastogram (ROTEM) locally.

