#### **4.1.7.1. Screening Period**

Potential participants will undergo the screening assessments described in the Schedule of Activities up to 6 ( $\pm 2$ ) weeks prior to the infusion of PF-06838435 once the consent process is completed at the vector-administration center. If the screening result of FIX:C activity level is  $>2\%$  due to recent infusion of factor IX protein product, then the severity of hemophilia B may be confirmed by documented historical evidence from a certified laboratory demonstrating the FIX:C activity level  $\leq 2\%$  or from a documented genotype known to produce a clinically severe phenotype of hemophilia B. If FIX:C activity is not  $\leq 2\%$  at screening or documented historical evidence is not available and genotype are not known, sample(s) will be drawn for analysis at Screening. Genotype is not a criterion for inclusion or exclusion. However, a documented genotype known to produce a clinically severe phenotype of hemophilia B is required if the participant is otherwise unable to demonstrate severity. Once the eligibility is verified, participants are required to undergo a washout of FIX protein products for at least 96 hours (4 days) prior to the Dosing Day (Day 0) to establish baseline value of FIX:C and FIX inhibitor. The screening period may be extended up to 2 weeks for participants who have a bleeding event requiring FIX protein product infusion within 96 hours prior to Day 0 (Dosing Day). If screening is prolonged greater than 8 weeks, then the FIX inhibitor, anti-AAV-Spark100 capsid antibody, biochemistry, hematology, vital signs, and physical examination screening assessments must be repeated to ensure continued eligibility. The reason for prolongation of screening should be clearly documented.

Screening assessments would also be done to verify participant eligibility are described in [Section 8.10.1](#).

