### 6.1.2. FIX Incremental Recovery of FIX Products

Participants should be reminded to have washout of at least 96 hours (4 days) without FIX protein product, or longer washout for extended half-life FIX protein product, prior to any blood draw and infusion on Day 0. On Day 0 participants will be infused with 100 IU/kg of their usual FIX protein product over 10 (±2) minutes, under the supervision from the site staff and/or Investigator(s) to assess FIX incremental recovery. Number of vials, total volume, and total dosage are monitored and recorded by the site staff.

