3.1. Overall Study Design and Plan

This is a Phase 1/2a, open-label, non-randomized, dose-escalation and multi-center study to evaluate the safety, tolerability, and kinetics of a single intravenous infusion of PF-06838435 in hemophilia B subjects with ≤ 2 IU/dL [$\leq 2\%$] endogenous factor IX [FIX]).

Approximately 15 evaluable subjects will be dosed with a single intravenous infusion of PF-06838435 at one of three different dose levels.

Subjects will provide informed consent and then undergo screening assessments up to 6 (± 2) weeks prior to PF-06838435 infusion on the Dosing Day (Day 0). All dosed subjects will undergo safety observation for a total of 52 (± 2) weeks after PF-06838435 infusion (see the Schedule of Events). Subjects who complete 52 (± 2) weeks (End-of-Study) will be encouraged to enroll in an extension study evaluating the long-term safety of PF-06838435 for up to an additional 5-year long-term follow-up (LTFU).

The administration of PF-06838435 to the first two subjects in the starting dose level will be staggered by at least two (2) weeks to ensure safety. Additionally, at least eight weeks of safety data from at least three (3) out of five (5) subjects in a given dose level will undergo review by an independent Data Monitoring Committee (DMC) prior to dosing the first subject in the next dose level.

There will be no dose escalation if at least three (3) subjects in any dose level achieve steady-state vector-derived FIX activity levels of $\geq 40\%$. Steady-state levels are based on an average of vector-derived FIX:C activity level measurements starting from Week 12 with adequate washout (i.e., 96 hours for pd- or r-FIX and up to 168 hours for extended half-life rFIX) from FIX product.

Originally, up to five (5) evaluable subjects may be dosed in each dose level. An initial dose level may be expanded up to ten (10) evaluable subjects if at least three (3) out of five (5) subjects achieve detectable steady-state vector-derived FIX activity levels above 5%. If, after the above initial dose-level expansion, at least six (6) out of ten (10) subjects achieve detectable steady-state vector-derived FIX activity levels above 5%, then further dose level expansion of up to ten (10) additional evaluable subjects would be allowed (a total of up to twenty evaluable subjects at the starting dose level of 5×10^{11} vg/kg).

The decision to dose escalate will require the agreement of the Sponsor and the DMC.

CCI
[Redacted text block]

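### Adequate washout for extended half-life FIX is given only as an upper bound, so a post-vector reading that still contains product can count as vector-derived steady-state FIX:C

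*Protocol*

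**What the plan says.** **Steady state and the dose rules.** Protocol 4.1.3.1 bases steady state on two vector-derived FIX:C readings at least two weeks apart, starting from Week 8-12, after adequate washout. That means 96 hours for plasma-derived or standard recombinant FIX, "and up to 168 hours for extended half-life recombinant factor IX". SAP 3.1 averages readings from Week 12 under the same condition: "96 hours for pd- or r-FIX and up to 168 hours for extended half-life rFIX". These levels decide whether escalation is ruled out (at least 3 participants at 40% or more), whether it occurs (fewer than 3 between 3% and 40%), and whether a dose level may expand (3 of 5, then 6 of 10, above 5%).

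**Day 0.** The statements differ:

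- Schedule of Activities (SoA) note 2 sets a floor of 96 hours for regular product, "or up to 168 hours [7 days] washout period for extended half-life factor IX products".
- SoA note 17 says "up to 168 hours (7 days) washout of extended half-life FIX product".
- Protocol 4.1.4 says "or up to approximately 168 hours of washout for extended half-life rFIX prior to FIX incremental recovery test".
- Protocol 4.1.7.1 covers every product: "participants are required to undergo a washout of FIX protein products for at least 96 hours (4 days) prior to the Dosing Day".
- Protocol 6.1.2 sets a floor of 96 hours, "or longer washout for extended half-life FIX protein product, prior to any blood draw and infusion on Day 0". It gives no figure for EHL, and SAP 3.3 is worded in the same way.
- SoA note 1 extends screening only when a bleed needs FIX within 96 hours of Day 0.

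**Intent.** The estimand (Protocol 3 and 9.1.1) is FIX:C unaffected by intercurrent FIX infusions.

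**The concern.** In the Day 0 passages standard product has a floor, while EHL product, which the protocol itself treats as needing longer, mostly has a ceiling. For post-vector samples the ceiling is the only EHL criterion in the visible text. A reading 48 hours after an EHL dose then satisfies the numeric rule, although it conflicts with the estimand.

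The route for contamination is open. Protocol 6.5.1 allows FIX as needed after the vector. SoA note 14 has FIX:C monitored two or three times a week through Week 12, which overlaps the start of the protocol's steady-state window. Protocol 4.1.4 and 8.5 use a one-stage assay both for exogenous FIX and for all plasma FIX activity, and no visible rule separates residual product from vector-derived activity. Inclusion criterion 2 accepts that insufficient washout can lift a reading above 2%.

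At stake is upward bias in a secondary endpoint and, less probably, in the counts behind escalation and expansion.

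**Working it through.** **1. What each rule requires of an EHL user**

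| Sample | Place | EHL requirement |
|---|---|---|
| Post-vector steady state | Protocol 4.1.3.1; SAP 3.1 | at most 168 h; no minimum |
| Day 0 | SoA notes 2 and 17; Protocol 4.1.4 | at most (about) 168 h |
| Day 0 | Protocol 4.1.7.1 | at least 96 h, all products |
| Day 0 | Protocol 6.1.2; SAP 3.3 | longer than for standard product; no figure |

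Day 0 therefore has an implied floor of 96 h. For post-vector samples no floor is visible. EHL product given 100 h before Day 0 meets every Day 0 line above and triggers no extension under SoA note 1.

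**2. Residual product**

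The plan states no residual figure, so there is none to reproduce. The documents also give no half-life, recovery or as-needed dose, so the inputs below are assumptions. Residual = post-dose level × 2^(−t/T), with T the half-life.

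| Assumed T and level | 96 h | 168 h |
|---|---|---|
| 70 h, 40% | 40 × 2^(−96/70) = 15.5% | 40 × 2^(−168/70) = 7.6% |
| 90 h, 70% | 70 × 2^(−96/90) = 33.4% | 70 × 2^(−168/90) = 19.2% |
| 110 h, 100% | 100 × 2^(−96/110) = 54.6% | 100 × 2^(−168/110) = 34.7% |
| 48 h, 50 IU/kg at recovery 0.6–1.0 IU/dL per IU/kg (30–50%) | 7.5–12.5% | 2.7–4.4% |

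At 48 h the first and third rows leave 24.9% and 73.9%. On the full grid (T 70, 90, 110 h; level 40, 70, 100%), only 2 of 9 combinations exceed 40% at 96 h, both with a level of 100%. For standard FIX with an assumed T of 18–24 h and level of 40–100%, the residual at 96 h is about 1 to 6%. The problem is mainly one for EHL users.

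**3. Is the Day 0 FIX infusion the source?**

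No. Week 8 is 8 × 7 × 24 = 1344 h later, and 100 × 2^(−1344/110) is about 0.02%. Only as-needed EHL use shortly before a sample matters.

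**4. Effect on an average**

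One affected reading with residual R among k readings raises an arithmetic mean by R/k. With R = 15 points, the shift is 15/2 = 7.5 points for two readings. Over the nine scheduled visits from Week 12 to Week 52 it is 15/9 = 1.7 points. SAP 10.2 uses geometric means, where the shift is not additive but is still upward.

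**5. Effect on the gates (illustration only)**

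Suppose 30% truly exceed 5% and 10% of the rest are misclassified. Both figures are assumptions. The apparent proportion is 0.30 + 0.70 × 0.10 = 0.37. Binomial tails:

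- P(at least 3 of 5) rises from 0.163 to 0.267.
- P(at least 6 of 10) rises from 0.047 to 0.121.

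**6. Direction at baseline**

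The 5% and 40% limits are absolute, so baseline does not enter them. A contaminated baseline acts only on the rules that compare a participant with his own baseline and on change-from-baseline comparisons. There it hides expression.

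**The case against.** The strongest reply is that this is loose wording whose intent is plain. Adequate washout, vector-derived activity and the estimand all point to product-free readings, and 6.1.2 shows that EHL is meant to need more time than standard product. It would be wrong to infer that the plan intends a 48 h EHL reading to count, or that it bars longer washouts. That stands as to intent, but the only EHL figure given for post-vector samples does not enforce the intent.

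Several safeguards also stand. Prophylaxis is suspended. The protocol needs two readings two weeks apart, so a non-expresser would normally need recent EHL use before both. The gates need several participants. Frequent sampling should yield cleaner readings, and the infusion log is reviewed at visits. Escalation needs sponsor and DMC agreement, and expansion is optional. The Schema notes say that no escalation occurred before Amendment 7.

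At Day 0 a grossly raised value would stand out against the 2% entry criterion. The SAP takes as baseline the last measurement usable for analysis, which leaves room to reject such a value, although usable is not defined. SoA note 2 also forbids thawing the product before washout is confirmed, so the 100 h example does not prove that dosing would go ahead.

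Finally, parts of both documents are blacked out, and the Schema refers to a section 4.1.3.2 that cannot be read. A sample-exclusion rule may exist there. The point is therefore limited to the visible text.

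**Conclusion.** The wording defect is established from the documents. The steady-state rule has an upper bound where it needs a lower one, no visible rule excludes affected readings, and the Day 0 passages do not agree. The consequence most likely to matter is upward bias in steady-state FIX:C among participants who use EHL product as needed, since one affected reading is enough to cause some. An effect on the 3%, 5% and 40% counts is possible.

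The size is not established. The 15 to 55% (96 h) and 8 to 35% (168 h) ranges depend on assumed half-lives and levels, and the 48 h case gives about 3 to 4% at 168 h. How many participants use EHL product is not stated.

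A reader might infer three stronger things that the documents do not support:

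- **That the expansion or escalation decisions are likely to be false.** A wholly false count would need contamination in several participants, normally at both readings in each, while prophylaxis is suspended.
- **That a contaminated baseline feeds the 5% and 40% rules.** It does not enter them.
- **That rewriting the existing 168 hours as a minimum settles the matter.** Under the longer assumed half-lives the residual at 168 h is still above 5%.

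**What to change.** 1. Reconcile SoA notes 1, 2 and 17, Protocol 4.1.3.1, 4.1.4, 4.1.7.1 and 6.1.2, SAP 3.1 and 3.3, and the schematic notes (Protocol 1.2, SAP Appendix 1) to one product-specific washout statement expressed as a minimum interval. The value is for the sponsor to set and justify; none is proposed here.
2. In Protocol 4.1.3.1 and the SAP, exclude any reading inside that interval from baseline, from steady state and from the 3%, 5% and 40% counts.
3. In the SAP, use the infusion log (product, date, dose) to report a sensitivity rerun of steady state and the gate counts without readings that follow recent EHL use, with the look-back period defined in advance.

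The cost is protocol and SAP wording and one additional analysis from data already collected. The downside is that a few readings are lost or must be repeated at the next visit.

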### **Study Design**

This is a Phase 1/2a, open-label, non-randomized, uncontrolled, dose-escalation and multi-center study to evaluate the safety, tolerability, and kinetics of a single IV infusion of PF-06838435 in hemophilia B participants with  $\leq 2$  IU/dL [ $\leq 2\%$ ] endogenous factor IX [FIX] levels. Up to 30 evaluable participants will be dosed with a single IV infusion of PF-06838435 at one of three different dose levels.

Participants will provide informed consent and then undergo screening assessments up to 6 ( $\pm 2$ ) weeks prior to PF-06838435 infusion on the Dosing Day (Day 0). All dosed participants will undergo safety observation for a total of 52 ( $\pm 2$ ) weeks after PF-06838435 infusion (see the Schedule of Activities). Participants who complete 52 ( $\pm 2$ ) weeks (End-of-Study) will be encouraged to enroll in an extension study evaluating the long-term safety of PF-06838435 for up to an additional 5 years.

Originally, up to 5 evaluable participants may be dosed in each dose level. An initial dose level may be expanded up to 10 evaluable participants if at least 3 out of 5 participants achieve detectable steady-state vector-derived FIX activity levels above 5%. If, after the above initial dose-level expansion, at least 6 out of 10 participants achieve detectable steady-state vector-derived FIX activity levels above 5%, then further dose-level expansion of up to 10 additional evaluable participants would be allowed (a total of up to twenty evaluable participants at the starting dose level of  $5 \times 10^{11}$  vg/kg). The administration of PF-06838435 to the first two participants in the starting dose level will be staggered by at least 2 weeks to ensure safety. Additionally, at least eight weeks of safety data from at least 3 out of 5 participants in a given dose level will undergo review by an independent data monitoring

[figure not shown]
committee (DMC) prior to dosing the first participant in the next dose level. Thus, there will be at least 8 weeks of staggering administration between dose levels.

CCI [REDACTED]

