## 1.2. Schema

Figure 1. Study Schematic

- 96 hours (4 days) washout for plasma derived (pd)- or rFIX [or up to 168 hours (7 days) washout for extended half-life rFIX]
- FIX incremental recovery for FIX products up to 24 (±1) hours after the infusion of the FIX products.
- First two participants at the starting dose level will be infused at least 2 weeks apart.
- The first two participants will be infused at least 8 weeks apart. As dose escalation did not occur during the course of this study prior to this amendment (v.7) participants entering the study (low antibody positive) will begin at this dose level. These participants will be dosed at 8-week intervals. If dose escalation occurs, the 8-week interval will remain.

\* Dose escalation criteria for starting dose 5x10^11 vg/kg group or 1x10^12 vg/kg group are described in [Section 4.1.3.2](#)

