#### **4.3. Justification for Dose**

Non-clinical pharmacology, toxicology, and biodistribution studies of AAV-Spark100-hFIX19-Padua have been performed in three animal models (wild-type [WT] mice, HB mice, and NHPs) to evaluate expression and safety. PF-06838435 has also been infused into NHP and demonstrated to drive expression of FIX at levels equivalent to AAV-Spark100-hFIX19-Padua. Long-term safety and immunogenicity of the FIX-Padua protein were evaluated in a hemophilic canine model using an AAV8-FIX-Padua vector. These data are relevant to PF-06838435 since FIX gene delivery using AAV-Spark100 results in similar levels of expression as compared to gene delivery using AAV8 in these species. Based on the Sponsor's experience, studies in mice have not been predictive of FIX expression levels in humans, but studies in dogs and NHPs have correlated well with levels in human participants. The non-clinical studies in NHP using AAV Spark100-hFIX19-Padua infused at a dose of  $1 \times 10^{12}$  vg/kg resulted in steady-state vector-derived FIX activity levels of  $\sim 27\%$  (range 22.7-30.7%).

A dose of  $5 \times 10^{12}$  vg/kg was administered without evidence of adverse effects in NHPs. It is widely accepted that maintaining factor activity levels above 1-2% of normal may prevent bleeding and ultimately arthropathy in patients with severe hemophilia. Based on large

animal models of the disease and prior clinical experience with AAV8-hFIX19, the starting dose of  $5 \times 10^{11}$  vg/kg may result in detectable circulating vector-derived factor IX (FIX:C) activity levels above background levels. This starting clinical dose ( $5 \times 10^{11}$  vg/kg) is ~10 fold lower than the highest dose studied in the Good Laboratory Practice (GLP) toxicology study. Furthermore, non-clinical safety data demonstrate that doses of  $1 \times 10^{12}$  vg/kg,  $2 \times 10^{12}$  vg/kg and  $5 \times 10^{12}$  vg/kg are generally well tolerated in NHPs and support the proposed up to three dose levels of  $5 \times 10^{11}$ ,  $1 \times 10^{12}$ , and  $2 \times 10^{12}$  vg/kg to be investigated in this study.

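### Escalation scenario 2 in protocol 4.1.3.1 leaves out responders above 40%, so three outcomes with 3 or 4 of 5 participants at 3% or more still call for a higher dose

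*Protocol*

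**What the plan says.** Five visible rules bear on the same dose cohort.

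- **Escalation scenario 2 (protocol 4.1.3.1).** The trigger is "If less than 3 evaluable dosed participants in a given dose level achieve steady-state vector-derived FIX activity levels between 3% to 40% of normal". The same sentence goes on to the consequence: "between 3% to 40% of normal, then escalation to the next dose level will occur, provided there are no safety concerns".
- **The bar (4.1.3.1).** "There will be no dose escalation if at least 3 participants in any dose level achieve steady-state vector-derived FIX activity levels of" 40% or more.
- **Agreement (4.1.3.1).** "The decision to dose escalate will require the agreement of Pfizer and DMC".
- **Cohort size.** Under expansion scenario 1 in 4.1.3.1, if at least one of the first two participants at the low or middle dose rises above baseline, "then up to an initial 5 evaluable participants will be dosed at the respective dose". The synopsis agrees: "Originally, up to 5 evaluable participants may be dosed in each dose level".
- **Expansion scenario 3 (4.1.3.1).** If at least 3 of 5 are above 5%, the level may grow to 10. This rule has no upper limit on activity.

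SAP 3.1 repeats the 40% bar and the need for sponsor and DMC agreement. It contains no version of scenario 2. The schema (protocol 1.2) reports that no escalation had taken place before Amendment 7. Its footnote places the escalation criteria for the 5x10^11 and 1x10^12 vg/kg groups in Section 4.1.3.2, which is redacted.

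**The concern.** The evident purpose of scenario 2 is to move up when too few participants respond. Its upper limit works against that purpose, because a participant above 40% is left out of the count just as one below 3% is.

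The effect shows when one participant's result changes. Take 5 evaluable participants with 2 below 3% and 3 in the 3-40% band. Scenario 2 is not met. Now let one of the three rise above 40%, and scenario 2 is met. A better response has turned the written rule towards a higher dose. The 40% bar shows that the sponsor wants high expression to stop escalation, so the two sentences pull in opposite directions until a third participant reaches 40%.

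The vector is infused once and cannot be withdrawn, so a trigger for a higher dose should not be met because some responses were high.

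**Working it through.** **Inputs.** The trigger, the bar and the cohort size of 5 come from protocol 4.1.3.1, the last also from the synopsis. The plan states no figure to reproduce, since the study tests no hypothesis.

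**Step 1: set up.** Let L, M and H be the numbers below 3%, from 3% to 40%, and above 40%, with L + M + H = 5. There are 21 such splits. Scenario 2 is met when M < 3. The bar applies when H ≥ 3 and is taken to override scenario 2, which is the reading most favourable to the plan.

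**Step 2: classify.**

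| Splits | Condition | Number |
|---|---|---|
| Scenario 2 not met | M ≥ 3 | 6 |
| Met, too few responders (evident intent) | M + H < 3 | 6 |
| Met, but stopped by the bar | M < 3 and H ≥ 3 | 6 |
| Met, not stopped, 3 or more at ≥3% | M ≤ 2, H ≤ 2, M + H ≥ 3 | 3 |
| Total | | 21 |

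Scenario 2 is met in 6 + 6 + 3 = 15 splits. The last row allows only (M,H) = (2,2), (1,2) and (2,1), so (L,M,H) is:

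- (1,2,2): 4 of 5 at ≥3%
- (2,1,2): 3 of 5 at ≥3%
- (2,2,1): 3 of 5 at ≥3%

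If all 5 reach 3% and M ≤ 2, then H ≥ 3 and the bar applies, so 5 of 5 never escalates. A value of exactly 40% falls in both bands as written. That does not remove any of the three splits when the top participants are above 40%.

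**Step 3: overlap with expansion scenario 3.** Everyone above 40% is also above 5%. At least 3 of 5 exceed 5% in (1,2,2) if one of the two mid-band participants does, in (2,1,2) if the single one does, and in (2,2,1) if both do. The cohort then meets an escalation rule and an expansion rule together, and no visible sentence says which comes first.

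**Step 4: how likely.** The documents give no band probabilities, so the values here are assumptions: independent participants at one dose, with probabilities l, m and h for the three bands. Each split has coefficient 5!/(1!2!2!) = 30, so

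P = 30lm²h² + 30l²mh² + 30l²m²h = 30·l·m·h·(mh + lh + lm).

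| l, m, h | Calculation | P |
|---|---|---|
| h = 0 | – | 0% |
| 0.05, 0.90, 0.05 | 30 × 0.00225 × 0.0925 | 0.6% |
| 0.10, 0.80, 0.10 | 30 × 0.008 × 0.17 | 4.1% |
| 0.20, 0.60, 0.20 | 30 × 0.024 × 0.28 | 20.2% |
| 1/3 each (maximum) | 30 × 1/27 × 1/3 = 30/81 | 37.0% |

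Protocol 4.3 reports about 27% ("range 22.7-30.7"%) in primates at 1x10^12 vg/kg, twice the starting dose. All of those values lie inside the 3-40% band, which favours the low end. Sections 1.1 and 2.1 cite six human participants given another FIX-Padua vector, with levels from below 1% to about 60%. Both outer bands are therefore possible in people, but those six were spread over three doses, so they do not show the spread within one dose.

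**Step 5: with the upper limit removed.** Scenario 2 becomes M + H < 3. It is met in 6 of 21 splits, none of them among the three above. The bar cannot conflict with it, because H ≥ 3 implies M + H ≥ 3.

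**The case against.** The strongest reply is that this sentence may no longer govern. The schema footnote sends the reader to 4.1.3.2 for the criteria at the two lower dose levels, and with three levels those are the only ones from which escalation is possible. That section is redacted, and the figure is not shown, so it is unclear where the footnote attaches. This stands: the point can be made only about the visible rule in 4.1.3.1.

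Second, escalation is not automatic, and expansion scenario 3 often offers an alternative for the same cohort. This stands as a limit on harm. It does not correct the trigger: escalation is worded as mandatory once safety is clear, expansion only as permitted, and those who must agree are left to choose between two rules.

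Third, each of the three splits needs someone below 3% and someone above 40% at the same dose, which may be rare. That is fair. The count of 3 in 21 is not a likelihood, and 37.0% is a ceiling rather than an expectation.

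A reader might also infer that scenario 2 is always met after the first two participants, since 2 is fewer than 3. The documents do not support that. Escalation scenario 1 and expansion scenario 1 already decide what happens after two participants at the levels from which escalation is possible.

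**Conclusion.** The point holds for the visible text of 4.1.3.1 and is minor. With 5 evaluable participants and the 40% bar overriding, exactly three of 21 splits call for escalation although 3 or 4 of 5 reached at least 3%. Neither the rest of the visible protocol nor SAP 3.1 repairs this. The count follows from the wording alone. Any probability rests on assumed band frequencies and independence, and the primate data suggest a small one.

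A reader might infer that good responders would be followed by an unsafe dose increase, or that the plan as a whole lacks a sound escalation rule. Neither follows. The safety proviso and the sponsor and DMC agreement stand between the trigger and a higher dose, no escalation had occurred before Amendment 7, and the redacted section may hold the criteria now in force. The schema does still provide for escalation under Amendment 7, so the sentence should say what is meant.

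**What to change.** In escalation scenario 2, replace the 3-40% band with *≥3% of normal*, and keep the 40% sentence as the overriding bar. State whether escalation or expansion takes precedence if a cohort can still meet both. If 4.1.3.2 replaces this rule, say so in 4.1.3.1.

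Do not make the rule wait for 5 evaluable participants with steady-state values. Once three are below 3%, at most 5 − 3 = 2 can reach 3%, so the answer is settled. Waiting would mean two more single-administration doses at a level that has already failed. Protocol 9.3 also defines evaluable as all dosed, and 7.2 provides replacement only for those who withdraw undosed, so one dosed participant lost before steady state could stall the rule. If a denominator is wanted, say that escalation applies once 3 of up to 5 participants are below 3%. With 5 evaluable this selects the same 6 splits.

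The cost is a short wording change in one section, with no added participants, procedures or analyses.
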